- d A minimum of 24 hours is required between doses during sequential dosing weeks (eg, C1D1-C1D5; C2D1-C2D5). Infusions of BMS-986277 on Day 3 and Day 5 must be administered within 7 days of Day 1.
- e EOT visit is C26D29 ( $\pm$  7 days) or at the time of study treatment discontinuation. If within 7 days prior to FU Visit 1, the EOT visit may be skipped and FU Visit 1 should be completed and include all EOT biomarker samples.
- f Dosing for the initial 2 participants into each dose level in Part 2 will be staggered by at least 7 days between participants (see [Section 5.1.2](#)).

**Table 2-4: On-Treatment Assessment Schedule (Combination Expansion - BMS-986277 and Nivolumab [Part 3 Cohorts 1-2])(CA034001)**

Procedures a	Cycle 1 (28 days) b				Cycle 2 (28 days) b				Cycle 3 and each subsequent cycle (28 days; Nivolumab only) c			Notes		
	D1 d	D3 d and D5 d	D8 ( $\pm 3$ days)	D15 ( $\pm 3$ days)	D22 ( $\pm 3$ days)	D1 d ( $\pm 3$ days)	D3 d and D5 d	D8 ( $\pm 3$ days)	D15 ( $\pm 3$ days)	D22 ( $\pm 3$ days)	D1 ( $\pm 3$ days)		D15 ( $\pm 3$ days)	EOT e
Safety	■	■	■	■	■	■	■	■	■	■	■	■	■	
Targeted PE, Physical Measurements, Vital Signs, ECOG Performance Status	X	X	X	X	X	X	X	X	X	X	X	X	X	On each BMS-986277 dosing day, assessments (vital signs) will be performed at predose, and every 15 minutes ( $\pm 5$ minutes) until 60 minutes following completion of infusion and then at 4 hours ( $\pm 30$ minutes) and 8 hours ( $\pm 1$ hour) postdose. See note in Table 2-1. On each nivolumab dosing day, vital signs will be performed at predose only.

**Table 2-4: On-Treatment Assessment Schedule (Combination Expansion - BMS-986277 and Nivolumab [Part 3 Cohorts 1-2])(CA034001)**

Procedures a	Cycle 1 (28 days) b				Cycle 2 (28 days) b				Cycle 3 and each subsequent cycle (28 days; Nivolumab only) c			Notes		
	D1 d	D3 d and D5 d	D8 ( $\pm 3$ days)	D15 ( $\pm 3$ days)	D22 ( $\pm 3$ days)	D1 d ( $\pm 3$ days)	D3 d and D5 d	D8 ( $\pm 3$ days)	D15 ( $\pm 3$ days)	D22 ( $\pm 3$ days)	D1 ( $\pm 3$ days)		D15 ( $\pm 3$ days)	EOT e

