#### 4 OBJECTIVES AND ENDPOINTS

**Table 4-1: Objectives and Endpoints**

Objectives	Endpoints
Primary	

 
To characterize the safety and tolerability of BMS-986277 administered alone and in combination with PD-1 inhibitor, nivolumab, in advanced epithelial tumors
 
To determine the RD and RP2D and dosing schedule of BMS-986277 administered alone and in combination with nivolumab in participants with advanced epithelial tumors
 
	
 
Incidence of AEs, SAEs, AEs meeting protocol-defined DLT criteria, AEs leading to discontinuation, and AEs resulting in death
 
Incidence of clinical laboratory test abnormalities
 
Vital sign abnormalities or other safety biomarkers
 

Secondary	

 
To explore the preliminary anti-tumor activity of BMS-986277 alone and in combination with nivolumab in participants with advanced epithelial tumors (RECIST v1.1 and PCWG3)
 
To assess the PK and IMG of BMS-986277 in blood following monotherapy or combination treatment
 
	
 
ORR, DCR, mDOR, mPFS, and PFSR at 8, 16, and 24 weeks depending on indication
 
Summary measures of PK and IMG parameters of BMS-986277
 

Abbreviations: AE = adverse events; BICR = blinded independent central review; DCR = disease control rate; DLT = dose-limiting toxicity; IMG = immunogenicity; iRECIST = immune Response Evaluation Criteria in Solid Tumors; mDOR = median duration of response; mOS = median overall survival; mPFS = median progression-free survival; NPV = negative predictive value; ORR = objective response rate; OS = overall survival; OSR = overall survival rate; PCWG3 = Prostate Cancer Clinical Trials Working Group 3; PK = pharmacokinetics; PFSR = progression-free survival rate; PPV = positive predictive value; RD = recommended dose; RECIST = Response Evaluation Criteria in Solid Tumors; RP2D = recommended Phase 2 dose; SAE = serious adverse events; TPR = true positive rate

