#### 7.1.4 Combination Dose Escalation (Part 2)

**Table 7.1.4-1: Selection and Timing of Dose for Part 2**

Study Treatment	Unit dose strength(s)/Dosage level(s)	Dosage formulation Frequency of Administration	Route of Administration
BMS-986277	Dose < BLRM-RD a	C1 to C2: D1, D3, and D5 (up to 2 cycles of 28 days each)	IV
Nivolumab	480 mg	Day 15 Q4W up to 26 cycles	IV
BMS-986277	BLRM-RD b	C1 to C2: D1, D3, and D5 (up to 2 cycles of 28 days each)	IV
Nivolumab	480 mg	Day 15 Q4W up to 26 cycles	IV

a Dose lower than the BLRM-RD from Part 1

b BLRM-RD from Part 1

In Part 2, to mitigate against unexpected ADR, a staggered enrollment (sentinel participant) approach will be employed during combination dose escalation (see [Figure 5.1.2-1](#) and [Figure 5.1.2-2](#)).

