### 7.1.5 Combination Expansion (Part 3 Cohorts 1-2)

**Table 7.1.5-1: Selection and Timing of Dose for Part 3 Cohorts 1-2**

Study Treatment	Unit dose strength(s)/Dosage level(s)	Dosage formulation Frequency of Administration	Route of Administration
BMS-986277	RD a	C1 to C2: D1, D3, and D5 (up to 2 cycles of 28 days each)	IV
Nivolumab	480 mg	D15 Q4W up to 26 cycles	IV

a RD from Part 2.

Participants will receive BMS-986277 at the dose recommended from the combination escalation phase of the study.

On BMS-986277 dosing days, participants will receive antipyretic prophylaxis predose and postdose (see [Section 7.7.2](#)). This will generally be acetaminophen/paracetamol and/or ibuprofen at a dose and schedule to manage the participant’s clinical condition, providing that it follows the prescribing information for the product(s). Other medications, including diphenhydramine and indomethacin may be used in line with the study site’s standard practice providing they are not excluded concomitant medications (see [Section 7.7.1](#)). Corticosteroid use may be considered under certain circumstances but should be discussed with the Medical Monitor (or designee) prior to initiation.

Furthermore, at Day 1 of Cycle 2, participants will receive an antipyretic plus an H1-antagonist and, following approval from the Medical Monitor (or designee), hydrocortisone 100 mg IV (or equivalent) one hour prior to BMS 986277 dosing and approximately 3 hours postdose.

BMS-986277 and nivolumab will be administered by IV infusion using a syringe pump (nivolumab may also be administered using an infusion bag).

Infusion duration of BMS-986277 will be based on the dose level chosen for Part 2, and will match the infusion duration for that dose level in Part 1. BMS-986277 will be administered over 5 minutes except for the  $3 \times 10^{12}$  vp dose, which will be administered over 15 minutes.

Nivolumab is infused over 30 minutes. Study treatment preparation and administration are described in [Section 7.1](#).

Participants should receive nivolumab at a dose of 480 mg as an approximate 30 minute infusion on Day 15 of each treatment cycle until progression, unacceptable toxicity, withdrawal of consent, completion of up to 26 cycles of treatment, or the study ends, whichever occurs first. Participants should begin study treatment within 3 calendar days of treatment assignment.

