### **7.1.6 Monotherapy Expansion with Option for Subsequent Nivolumab Treatment (Part 3 Cohort 3)**

**Table 7.1.6-1: Selection and Timing of Dose for Part 3 Cohort 3**

Study Treatment	Unit dose strength(s)/ Dosage level(s)	Dosage formulation Frequency of Administration	Route of Administration
BMS-986277	RD a	C1 to C2: D1, D3, and D5 (up to 2 cycles of 28 days each)	IV
Optional: Nivolumab	480 mg	D1 Q4W up to 26 cycles starting at C3	IV

a RD from Part 1.

In Part 3 Cohort 3, participants will receive an IV infusion of BMS-986277 at the RD determined in Part 1, starting at time zero administered directly into the venous access point using a syringe pump on Days 1, 3, 5 of each cycle. BMS-986277 will be administered over 5 minutes except for the  $3 \times 10^{12}$  vp dose, which will be administered over 15 minutes. The RD from Part 1 will be determined as indicated in [Section 7.1.3](#). Participants should begin study treatment within 3 calendar days of treatment assignment.

On BMS-986277 dosing days, participants will receive antipyretic prophylaxis predose and postdose (see [Section 7.7.2](#)). This will generally be acetaminophen/paracetamol and/or ibuprofen at a dose and schedule to manage the participant's clinical condition, providing that it follows the prescribing information for the product(s). Other medications, including diphenhydramine and indomethacin may be used in line with the study site's standard practice providing they are not excluded concomitant medications (see [Section 7.7.1](#)). Corticosteroid use may be considered under certain circumstances but should be discussed with the Medical Monitor (or designee) prior to initiation.

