#### **9.5 Pharmacokinetics**

Samples for PK and IMG assessments will be collected for all participants receiving BMS-986277 as monotherapy and in combination with nivolumab. PK of BMS-986277 will be characterized by noncompartmental analysis method using a validated PK analysis program. Data may be pooled with other future studies for PPK analysis of BMS-986277, the results of which will be reported in a separate pharmacometric report.

The PK parameters of BMS-986277 to be assessed following C1D1 dose administration, if data permit, include:

C max	Maximum observed blood concentration
T max	Time of maximum observed blood concentration
AUC(0-T)	Area under the blood concentration-time curve from time zero to time of last quantifiable concentration
AUC(INF)	Area under the blood concentration-time curve from time zero extrapolated to infinite time
T-HALF	Apparent terminal half-life
CLT	Total body clearance
V ss	Volume of distribution at steady-state
V z	Volume of distribution of the elimination phase

The PK parameters of BMS-986277 to be assessed following C1D15 and C1D19 doses (Part 1 monotherapy), C1D1 and C1D5 doses (Part 3 Cohort 3), and C1D1 and C1D5 doses (Part 2 and Part 3 Cohorts 1-3 BMS-986277 and nivolumab therapy), if data permit, include:

C max	Maximum observed blood concentration
T max	Time of maximum observed blood concentration

AUC(0-T)	Area under the concentration-time curve from time zero to time of last quantifiable concentration
AUC(0-48)	Area under the concentration-time curve from time zero to 48 hours postdose
AUC(0-8)	Area under the concentration-time curve from time zero to 8 hours postdose
C48	Blood concentration 48 hours postdose

In addition, the PK parameters of BMS-986277 listed below may be assessed, if data permit, following the C1D19 dose (monotherapy) and C1D5 dose (combination therapy):

CLT	Total body clearance
C ss -avg	Average blood concentration over a dosing interval at steady state (AUC[0-48]/48)
AI_AUC	AUC accumulation index; ratio of AUC(0-48) on Cycle 1 Day 19 to AUC(0-48) on Cycle 1 Day 15 for monotherapy, and ratio of AUC(0-48) on Cycle 1 Day 5 to AUC(0-48) on Cycle 1 Day 1 for combination therapy

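### Most BMS-986277 PK parameters labelled as combination therapy are measured before the first nivolumab dose, and Cohort 3 lacks the 48 h sample its parameters require

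*Protocol*

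**What the plan says.** The secondary PK objective in Protocol Table 4-1 is "To assess the PK and IMG of BMS-986277 in blood following monotherapy or combination treatment". The endpoint is summary measures of the PK parameters.

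Section 9.5 names Cmax, Tmax, AUC(0-T), AUC(0-48), AUC(0-8) and C48 for "C1D1 and C1D5 doses (Part 2 and Part 3 Cohorts 1-3 BMS-986277 and nivolumab therapy". It adds CLT, Css-avg, the two accumulation indices and two half-lives after the C1D5 dose for combination therapy. The AUC index is defined as the "ratio of AUC(0-48) on Cycle 1 Day 5 to AUC(0-48) on Cycle 1 Day 1 for combination therapy". Ctrough is listed separately, with no restriction to Cycle 1. All of these parameters are conditional on the data permitting, except Ctrough, which is simply to be reported.

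Dosing in Part 2 (Table 7.1.4-1) is "C1 to C2: D1, D3, and D5 (up to 2 cycles of 28 days each" for the virus and "Day 15 Q4W up to 26 cycles" for nivolumab. Part 3 Cohorts 1-2 follow the same pattern, with nivolumab on "D15 Q4W up to 26 cycles" (Table 7.1.5-1). In Cohort 3, nivolumab is optional and given "D1 Q4W up to 26 cycles starting at C3" (Table 7.1.6-1), after virus dosing has ended.

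SAP 5.2.2 repeats the parameter list. SAP 8.7.2 tabulates the parameters by part and dose level and plots Ctrough against cycle.

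**The concern.** A parameter reported under the heading of BMS-986277 with nivolumab should describe the virus in a participant who has received nivolumab. Here the doses that supply most of the parameters precede the first nivolumab infusion, so the label does not match the exposure.

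The stake is interpretation. Tables by part would set Part 1 monotherapy beside Part 2 and Part 3 combination. The two would tend to look alike because nivolumab was absent from both. A reader of the study report could take that likeness as evidence about nivolumab, which it cannot be.

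Cohort 3 has two further faults. It appears in Section 9.5 both on its own and within the combination list, for the same C1D1 and C1D5 doses. The section also asks for C48 and AUC(0-48) after C1D5, which the cohort's sampling table does not support.

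**Working it through.** The plan gives no figure to reproduce. The check is a timeline and a count of scheduled samples.

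**1. Cycle 1 virus doses against first nivolumab (Part 2, Part 3 Cohorts 1-2)**

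Inputs: virus on Days 1, 3 and 5; nivolumab on Day 15 with a window of ±3 days (Sections 7.1.2 and 7.1.4.1, Tables 2-3 and 2-4); and the rule "Infusions of BMS-986277 on Day 3 and Day 5 must be administered within 7 days of Day 1" (Table 2-3 footnote; Table 2-4 has the same).

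- Nominal: C1D1 is 15 − 1 = 14 days before nivolumab, and C1D5 is 15 − 5 = 10 days before.
- Extreme: the third dose is on Day 1 + 7 = 8, its 48 h interval ends on Day 8 + 2 = 10, and the earliest nivolumab is on Day 15 − 3 = 12.

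Every 0-48 h profile in Cycle 1 therefore closes before nivolumab.

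**2. Cycle 2 virus doses**

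Cycle 2 starts no sooner than 28 days after C1D1, so nominally on study Day 29. C2D1, C2D3 and C2D5 then fall 14, 16 and 18 days after first nivolumab. These are the only virus doses given after nivolumab.

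**3. Whole-blood virus samples in Table 9.5-2** (excluding end of treatment, follow-up and event-driven samples)

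| Period | Samples | Count |
|---|---|---|
| Before first nivolumab | C1D1 and C1D5: predose, EOI, 1, 2, 3, 4, 8 h (7 each); C1D3: predose, EOI; C1D7: 48 h; C1D15: predose | 14 + 2 + 1 + 1 = 18 |
| After first nivolumab | C1D22; C2D1, C2D3, C2D5: predose, EOI (2 each); C2D7: 48 h; C2D15: predose; C2D22 | 1 + 6 + 1 + 1 + 1 = 10 |

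None of the 10 later samples lies between end of infusion and 48 h after a Cycle 2 dose. They support troughs, an end-of-infusion value close to Cmax, and a 48 h concentration. A noncompartmental analysis, the stated method, cannot give an adequate AUC(0-8), AUC(0-48), CLT, half-life or AUC accumulation ratio from them.

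**4. Participants affected**

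Up to 36 in Part 2 and 40 + 40 in Part 3 Cohorts 1-2 (Section 5.2), so up to 116.

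**5. Cohort 3**

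Optional nivolumab starts at Cycle 3. Participants who progress early skip the remaining monotherapy visits. No virus dose follows nivolumab on either route.

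After C1D5, Table 9.5-3 samples at predose, EOI, 1, 2, 3, 4 and 8 h, then at 72 h on C1D8. C48 is not scheduled, and AUC(0-48) must be interpolated across 72 − 8 = 64 h. After C1D1 the C1D3 predose sample serves as the 48 h value, so the gap is confined to C1D5. Table 9.5-2 does schedule a 48 h draw on C1D7.

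**The case against.** A reader might infer that every combination PK parameter precedes nivolumab and that the objective goes unanswered. The documents do not support that. Ctrough is a listed parameter with no cycle limit, and the SAP plots it by cycle. Predose, end-of-infusion and 48 h samples are drawn in Cycle 2 after nivolumab, and the SAP summarises concentrations by nominal time. AUC(0-T) after C1D5 runs to the last quantifiable value, which could be the 408 h sample on C1D22, after nivolumab.

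A reader might also infer that the plan sets out to show no effect of nivolumab on the virus. No such comparison is planned in the visible text. Reporting is descriptive, Appendix 9 says no PK interaction is expected, and the interaction named for population PK is the reverse one. Population PK could use all samples, but it is optional and exploratory. Some rationale is redacted, so a reason for the sampling days may exist unseen.

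Moving the dense draws into Cycle 2 would have real costs. Only participants without a DLT or progression, and judged suitable, reach that cycle. A Cycle 2 profile would mix nivolumab with cycle number, antibodies to the virus and the different C2D1 premedication. Part 1 and Cohort 3 have only predose and end-of-infusion samples on C2D5, so there is no matched control.

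The Cohort 3 gap is small: one time point in about 12 participants, in a cohort whose stated aim is pharmacodynamic.

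These points narrow the finding and make resampling a matter of judgement. They do not justify reporting pre-nivolumab AUCs as combination PK, or requesting a C48 that has no sample.

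**Conclusion.** The point holds in a limited form. Apart from Ctrough, the sparse Cycle 2 concentrations and any AUC(0-T) tail reaching C1D22, the parameters that Section 9.5 assigns to combination therapy describe the virus before nivolumab. This applies to up to 116 participants, with at least 2 days between the end of the 48 h interval and nivolumab in the worst case (12 − 10) and 8 days nominally (15 − 7). The combination part of the secondary PK objective is answered only sparsely. It is not left wholly unanswered.

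Cohort 3 does not belong on the combination list. Its C48 after C1D5 is unscheduled for all of its approximately 12 participants.

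The conclusion assumes that dosing and sampling keep to the stated windows. It does not depend on whether nivolumab actually alters virus exposure, which the documents cannot show. The primary safety and dose-finding objectives are not affected.

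**What to change.** 1. **Labels.** In Protocol 9.5 and SAP 5.2.2 and 8.7.2, head the Cycle 1 parameters in Part 2 and Part 3 Cohorts 1-2 as *BMS-986277 before nivolumab*. Remove Cohort 3 from the combination list. Report the Cycle 2 trough, end-of-infusion and 48 h concentrations, with the late values from C1D22 onward, as the only virus PK with nivolumab on board. State that the Cycle 1 tables give no basis for concluding that nivolumab has no effect. This costs text only. The SAP needs revision anyway, since it incorporates changes only up to Revised Protocol 03 and describes two expansion cohorts.

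2. **Cohort 3 sampling.** In Table 9.5-3, replace the C1D8 72:00 PK draw with C1D7 48:00. Day 7 lies inside the Day 8 ± 3 visit window (Days 5 to 11). A third dose as late as Day 8 would put the draw on Day 10, also inside. The number of draws is unchanged. The price is the 72 h point, which leaves 240 h (C1D15) as the next sample.

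3. **Optional, for the sponsor to weigh.** In Table 9.5-2, move the five 1-8 h draws from C1D5 to C2D5. The closing 48 h sample on C2D7 already exists, so a post-nivolumab profile would need no extra draws. The costs are loss of the C1D5/C1D1 accumulation index in the combination groups and no multiple-dose profile in anyone who does not reach C2D5. The profile would also be confounded with cycle, antibodies and premedication unless a monotherapy group has matching C2D5 sampling, which would add draws there.

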a EOI = End of Infusion, This sample should be taken immediately prior to stopping the infusion (preferably less than 2 minutes prior to the end of infusion). If the end of infusion is delayed to beyond the nominal infusion duration, the collection of this sample should also be delayed accordingly.

b If within 3 days of other visits, the EOT samples may be skipped.

c If virus is detected at the 60 Day Follow-up visit, samples should continue to be collected at least every 30 days until virus is no longer detected.

Infusion duration: BMS-986277 will be administered over 5 minutes except for the  $3 \times 10^{12}$  vp dose, which will be administered over 15 minutes.

**Table 9.5-2: Pharmacokinetic (PK), Anti-Drug Antibody (ADA), and Shedding Sampling Schedule for Combination Dose Escalation (Part 2) and Combination Expansion - BMS-986277 and Nivolumab (Part 3 Cohorts 1-2)(CA034001)**

Study Day of Sample Collection	Event	Time (Relative To Start of Infusion of BMS-986277 Dose ) Hour: Min	BMS-986277 Whole Blood PK Sample	BMS-986277 Serum ADA Sample	Nivolumab Serum PK Sample	Nivolumab Serum ADA Sample	BMS-986277 Shedding Sample (urine)	BMS-986277 Shedding Sample (saliva)	BMS-986277 Shedding Sample (stool) ( $\pm$ 7 days)
C1D1, C2D1	predose	00:00	X	X			X	X	X
C1D1, C2D1	EOI a	00:15	X						
C1D1, C1D5		01:00	X						
C1D1, C1D5		02:00	X						
C1D1, C1D5		03:00	X						
C1D1, C1D5		04:00	X						
C1D1, C1D5		08:00	X						
C1D3, C2D3	predose	00:00	X				X	X	X
C1D3, C2D3	EOI a	00:15	X						
C1D5, C2D5	predose	00:00	X				X	X	X
C1D5, C2D5	EOI a	00:15	X						
C1D7, C2D7		48:00	X				X	X	X
C1D15, C2D15 b	predose	00:00	X	X	X	X c	X	X	X
C1D15, C2D15 b	EOI a	00:30			X				
C1D22, C2D22		408:00	X	X			X	X	X
C3D15 b	predose	00:00			X	X	X	X	X

**Table 9.5-2: Pharmacokinetic (PK), Anti-Drug Antibody (ADA), and Shedding Sampling Schedule for Combination Dose Escalation (Part 2) and Combination Expansion - BMS-986277 and Nivolumab (Part 3 Cohorts 1-2)(CA034001)**

Study Day of Sample Collection	Event	Time (Relative To Start of Infusion of BMS-986277 Dose ) Hour: Min	BMS-986277 Whole Blood PK Sample	BMS-986277 Serum ADA Sample	Nivolumab Serum PK Sample	Nivolumab Serum ADA Sample	BMS-986277 Shedding Sample (urine)	BMS-986277 Shedding Sample (saliva)	BMS-986277 Shedding Sample (stool) ( $\pm$ 7 days)
C3D15	EOI a	00:30			X				
C4D15, C8D15, C12D15 f	predose	00:00			X	X			
Grade 3/4 hypersensitivity reaction			X	X	X	X			
EOT d			X	X	X	X	X	X	X
Follow up visit 1			X	X	X	X	X	X	X
Follow up visit 2 e			X	X	X	X	X	X	X

a EOI = End of Infusion, This sample should be taken immediately prior to stopping the infusion (preferably less than 2 minutes prior to the end of infusion). If the end of infusion is delayed to beyond the nominal infusion duration, the collection of this sample should also be delayed accordingly.

b Samples are relative to the start of nivolumab infusion on these days.

c Nivolumab ADA samples are only needed at C1D15 predose.

d EOT visit is at the time of study treatment discontinuation. If within 3 days of other visits, the EOT samples may be skipped.

e If virus is detected at the 60 Day Follow-up visit, samples should continue to be collected at least every 30 days until virus is no longer detected.

f Nivolumab PK and ADA samples will continue to be collected every 16 weeks (4 cycles) until end of treatment.

**Table 9.5-3: Pharmacokinetic (PK), Anti-Drug Antibody (ADA), and Shedding Sampling Schedule for Monotherapy Expansion - BMS-986277 (Part 3 Cohort 3) Monotherapy with Option for Subsequent Nivolumab Therapy (CA034001)**

Study Day of Sample Collection	Event	Time (Relative To Start of Infusion of BMS-986277 Dose ) Hour: Min	BMS-986277 Whole Blood PK Sample	BMS-986277 Serum ADA Sample	Nivolumab Serum PK Sample	Nivolumab Serum ADA Sample	BMS-986277 Shedding Sample (urine)	BMS-986277 Shedding Sample (saliva)	BMS-986277 Shedding Sample (stool) ( $\pm$ 7 days)
C1D1, C2D1	predose	00:00	X	X			X	X	X
C1D1, C2D1	EOI a	00:15	X						
C1D1, C1D5		01:00	X						
C1D1, C1D5		02:00	X						
C1D1, C1D5		03:00	X						
C1D1, C1D5		04:00	X						
C1D1, C1D5		08:00	X						
C1D3, C2D3	predose	00:00	X				X	X	X
C1D3, C2D3	EOI a	00:15	X						
C1D5	predose	00:00	X				X	X	X
C1D5	EOI a	00:15	X						
C1D8, C2D8		72:00	X				X	X	X
C1D15, C2D15		240:00	X	X			X	X	X
C1D22, C2D22		408:00	X	X			X	X	X
C2D5	predose	00:00	X				X	X	X
C2D5	EOI a	00:15	X						
C3D1 b	predose	00:00 f	X	X	X	X	X	X	X

**Table 9.5-3: Pharmacokinetic (PK), Anti-Drug Antibody (ADA), and Shedding Sampling Schedule for Monotherapy Expansion - BMS-986277 (Part 3 Cohort 3) Monotherapy with Option for Subsequent Nivolumab Therapy (CA034001)**

Study Day of Sample Collection	Event	Time (Relative To Start of Infusion of BMS-986277 Dose ) Hour: Min	BMS-986277 Whole Blood PK Sample	BMS-986277 Serum ADA Sample	Nivolumab Serum PK Sample	Nivolumab Serum ADA Sample	BMS-986277 Shedding Sample (urine)	BMS-986277 Shedding Sample (saliva)	BMS-986277 Shedding Sample (stool) (± 7 days)
C3D1 b	EOI a	00:30 f			X				
C4D1 b	predose	00:00 f	X	X	X	X	X	X	X
C4D1 b	EOI a	00:30 f			X				
C8D1, C12D1, C16D1 e		00:00 f			X	X			
Grade 3/4 hypersensitivity reaction			X	X					
EOT c			X	X			X	X	X
Follow up visit 1			X	X	X	X	X	X	X
Follow up visit 2 d			X	X			X	X	X

a EOI = End of Infusion, This sample should be taken immediately prior to stopping the infusion (preferably less than 2 minutes prior to the end of infusion). If the end of infusion is delayed to beyond the nominal infusion duration, the collection of this sample should also be delayed accordingly.

b Samples are relative to the start of nivolumab infusion on these days. These samples are only collected if patients receive subsequent nivolumab therapy after 2 cycles of BMS-896277.

c EOT visit is at the time of study treatment discontinuation. If within 3 days of other visits, the EOT samples may be skipped.

d If virus is detected at the 60 Day Follow-up visit, samples should continue to be collected at least every 30 days until virus is no longer detected.

e Nivolumab PK and ADA samples will continue to be collected every 16 weeks (4 cycles) until end of treatment.

f Relative to nivolumab dose.

Infusion duration: BMS-986277 will be administered over 5 minutes except for the  $3 \times 10^{12}$ -vp dose, which will be administered over 15 minutes.

The whole blood PK samples will be analyzed for BMS-986277 by a validated qPCR assay. Serum samples will be analyzed for nivolumab and ADA (anti-BMS-986277 antibodies and/or anti-nivolumab antibodies) by validated immunoassays. Samples designated for PK or biomarker assessments may also be used for IMG analysis if required (eg, insufficient volume for complete IMG assessment or to follow up on suspected IMG related AE). Detailed instructions for the PK blood collection, labeling, processing, storage, and shipping will be provided to the site in the procedure manual.

Selected whole blood and serum samples may be analyzed by an exploratory orthogonal method that measures BMS-986277, infectivity, and/or anti-BMS-986277 antibodies. Potential results generated from any orthogonal method are intended as informational for technology exploration purposes and may be reported separately.

[figure not shown]
In addition, ad hoc serum samples designated for PK or biomarker assessments may also be used for IMG analysis if required (eg, insufficient volume for complete IMG assessment or to follow up on suspected IMG related AE).

